8.6 Follow-Up (Days 3, 7, & 14 ± 1 day)

- Collect the following data on participant:
 - Review adherence of antibiotic treatment recommendation.
 - Antibiotics prescribed (start and end dates, name, dose)
 - Microbiological results
 - Colonization status for MDRO
 - Signs and symptoms of infection
 - Adverse events related to antibiotics if any
 - Laboratory values for creatinine, liver, hematology

8.7 End of Study Visit EOSV (Day 28 + 2 days)

If participant is discharged prior to Day 28, provide a BAST-ICU discharge packet (28-day antibiotic use diary and report any symptoms). Every effort should be made to complete the Day 28 visit by conducting a remote call.

- Collect the following data on participant:
 - Review adherence of antibiotic treatment recommendation.
 - Antibiotics prescribed (start and end dates, name, dose)
 - Microbiological results
 - Colonization status for MDRO
 - Signs and symptoms of infection
 - Adverse events related to antibiotics if any
 - Laboratory values for creatinine, liver, hematology
 - Vital status: date of death, date of discharge from ICU, date of discharge from hospital
 - Disposition upon discharge from ICU

- Final clinical outcomes and DOOR ranking

8.8 Study Procedures common to both groups: Assessment of antibiotic prescription

Before recruitment of the first patient, the investigators at each site (MGH and RVH) ensure that all legal and regulatory requirements are met. No patients are to be screened or included until the trial starts by the project coordinator.

For all participants, the study team (Pharmacist and PI/Co-I) will review the medical chart and complete a standard prescription quality assessment form. All participants will have baseline data consisting of:

- Sociodemographic information
- Comorbidities, current medications
- Vital signs
- Test results and therapeutics relevant to current illness
- Antibiotics prescribed and received

Based on this assessment, they will arrive at a rating of the antibiotic prescription that includes 3 domains: Appropriateness of diagnostics, necessity of antibiotics, and choice of antibiotics.

8.9 Antibiotic treatment decision procedure specific to the control group

For the control group, the BV test result will remain masked to investigators and treating team members.

The antimicrobial stewardship study team (Pharmacist and PI/Co-I) will issue antibiotic treatment suggestions following the standard decision matrix outlined below. The recommendation will be shared with the treating team.

Necessity of antibiotics	Recommendation on antibiotic treatment
Clearly not indicated	STOP (strong recommendation)
Somewhat indicated	Stop (moderate recommendation) or continue --> review choice*
Indicated (Justified)	Continue antibiotic --> review choice *
Cannot be rated	Consider expert (ID) consultation

For all cases where necessity of antibiotics was rated as “somewhat indicated” or “indicated”, the choice of antibiotics will be rated. The final recommendation (to stop, continue or change antibiotic) is shared with the treating team.

Choice of antibiotic	Recommendation on antibiotic treatment
Far too broad	Change drug (strong recommendation)
Somewhat too broad	Consider changing drug (moderate recommendation)
Appropriate choice	Continue same drug
Somewhat too narrow	Change drug
Cannot be rated	Consider expert consultation (ID)

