1.2 Study Rationale

The central question of this study is whether a biomarker-signature -supported antibiotic treatment decision matrix can have a beneficial impact on antibiotic use and patient outcomes in an ICU population.

We propose to combine the evaluation of this test pragmatically with an antibiotic treatment decision matrix in a manner that mimics real-life but is as close as possible to a “best-case” scenario - modeling our study on a successful NIH-funded multicenter trial of PCT-guided use of antibiotics which avoided many of the biases that previously led to overestimating the benefit of PCT⁴². This study will inform researchers, practitioners, and health-care administrators whether and how this recently commercialized diagnostic assay should be incorporated in routine practice, ensuring diagnostic stewardship considerations are integrated within AMS considerations.

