3.2.2 Secondary Objective(s)

The assessment at 28 days will determine the overall effectiveness and safety of the intervention. To evaluate the following parameters:

- Antibiotic-free Days in ICU: The number of days patients remain in the ICU without antibiotic treatment.
- Use of Reserve/Restricted Antibiotics: The frequency and duration of the use of reserve or restricted antibiotics.
- Adherence to Recommendations: The degree of adherence to the recommended treatment guidelines and protocols.
- Incidence of Clinically Significant (Grade IV) Adverse Events: The occurrence of severe adverse events classified as Grade IV.
- Recurrent Infections: The rate of infection recurrence during the study period.
- Infectious Complications: The incidence of complications arising from infections.
- Length of Stay in ICU: The duration of the patient's stay in the intensive care unit.
- Death: The mortality rate during the study period.
- Colonization with Multi-Drug-Resistant Organisms: The incidence of colonization by multi-drug-resistant organisms.

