8.10 Antibiotic treatment decision procedure specific to the experimental group

The result of the BV test will be unmasked for the investigators and combined with the prescription assessment form using the decision matrix below. The final recommendation (to stop, continue or change antibiotic treatment) will be shared with the treating team.

Necessity of antibiotics	BV score < 35	BV $\geq 35 \leq 65$	BV > 65
Clearly not indicated	STOP*	STOP*	Expert consultation
Somewhat indicated	STOP*	STOP**	Continue ***
Justified	Expert consultation	Continue ***	Continue ***
Cannot be rated	STOP*	STOP**	Continue ***

*Strong recommendation; **Moderate recommendation; ***review choice of antibiotic

In all cases of “continue antibiotic treatment***”, rate the choice of antibiotic. The final recommendation (to stop, continue or change the antibiotic) will be shared with the treating team.

Choice of antibiotic:	Recommendation
Far too broad	Change drug
Somewhat too broad	Change drug
Appropriate choice	Continue same drug
Somewhat too narrow	Change drug
Cannot be rated	Expert consultation

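### Three of the five rows of the choice-of-antibiotic table differ between arms with no BV input, so differences in reserve-antibiotic use and adherence could not be credited to the BV test

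*Protocol*

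**What the plan says.** Section 8.8 describes a prescription assessment form used for every participant. The choice of antibiotic is one of its three rated domains.

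In the control arm (8.9), patients whose need for antibiotics is rated somewhat indicated or indicated go on to a second step in which "the choice of antibiotics will be rated". In the experimental arm (8.10), the second step applies only to the continue cells of the necessity-by-BV matrix. There the team is to "rate the choice of antibiotic. The final recommendation (to stop, continue or change the antibiotic) will be shared with the treating team".

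Both second-step tables list the same five ratings and neither has a BV column. The attached advice is not the same. For the middle grade of over-breadth the control table reads "Consider changing drug (moderate recommendation", and the experimental row reads "Somewhat too broad Change drug".

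Section 3.2.2 makes reserve or restricted antibiotic use a secondary objective, described as "The frequency and duration of the use of reserve or restricted antibiotics", and lists adherence to recommendations as another. Section 12.7 adds per-protocol analyses of cases in which the recommendations were followed. Section 1.2 says the study will inform "whether and how this recently commercialized diagnostic assay should be incorporated in routine practice".

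**The concern.** Control patients also receive advice from the study team under a standard matrix, so the choice table is a component that both arms share. A shared component with no BV input would be expected to be identical, leaving the arms to differ only where the BV result enters. It is not identical, and the protocol does not explain why.

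Two consequences follow. First, how firmly the advice to narrow is put may influence which drugs are used, and so may move reserve or restricted antibiotic use whatever the assay contributes. Second, the wording alters what counts as following the advice. Advice to consider a change can be met while keeping the drug; an instruction to change cannot. The same clinician behaviour could then be recorded as adherent in control and non-adherent in the experimental arm. That would distort the adherence comparison and the make-up of the per-protocol set.

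**Working it through.** The plan states no figure on this point, so there is none to reproduce. The check is a row-by-row comparison of the two tables, followed by an illustration on assumed values.

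**Rows side by side (8.9 against 8.10)**

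- Far too broad: control "Change drug (strong recommendation"; experimental gives the same instruction with no strength grade.
- Somewhat too broad: control "Consider changing drug (moderate recommendation"; experimental "Somewhat too broad Change drug" (row label and cell run together).
- Appropriate choice: keep the drug, in both arms.
- Somewhat too narrow: change the drug, in both arms.
- Cannot be rated: control "Consider expert consultation (ID"; experimental refers to an expert without the softening verb.

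Three of five rows differ. One differs in the action advised on the drug, one in the firmness of the referral, and one only in a missing grade. The experimental necessity matrix in 8.10 does grade its stop recommendations as strong or moderate, so grading is used in that arm but is absent from its choice table.

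**Where BV does enter.** The BV score decides who reaches the experimental choice table. A justified prescription with BV below 35 goes to expert consultation instead. The clean comparison is therefore a pair of patients both rated justified and somewhat too broad, with the experimental patient's BV at 35 or above. Both continue antibiotics and both reach the choice table, and the advice on the drug differs through allocation alone.

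**Illustration of size (assumed inputs)**

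- q = share of patients per arm who reach the table and are rated somewhat too broad: 10-30%.
- d = uptake of the instruction to change minus uptake of the advice to consider it: 10-30 percentage points.
- Between-arm difference in patients switched = q × d.
- Low end: 0.10 × 0.10 = 0.01, or 6 of 600 per arm.
- Middle: 0.20 × 0.20 = 0.04, or 24 of 600.
- High end: 0.30 × 0.30 = 0.09, or 54 of 600.

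The 600 per arm is from section 4.1. Neither q nor d can be obtained from the protocol.

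**The case against.** The strongest reply is that the protocol evaluates a BV-supported decision matrix, not the assay in isolation. The synopsis and section 3.1 define the contrast as the matrix plus standard of care against standard of care alone, and the central question in 1.2 is about the matrix. This stands. A reader might infer that the differing tables defeat a stated aim of isolating BV, or invalidate the primary comparison. The documents state no such aim, and the comparison of strategies is unaffected. What remains is attribution: 1.2 also speaks of the assay itself, and 1.3 ties the results to whether the BV test should be implemented. In one scenario 1.3 offers hospitals a choice between the test and clinical assessment of prescription quality.

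Other stronger readings also fail:

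- **Days of treatment.** It is tempting to say that firmer advice to change drug lowers the antibiotic-use measure. Section 12.3 sums days per drug, so a one-for-one swap leaves the total unchanged. It moves only if a change drops an agent or alters duration. The final test in 12.9 compares mean duration, which a swap does not in itself alter.
- **Uniformly firmer advice in the experimental arm.** The row for far too broad runs the other way: only control carries an explicit strong grade.
- **A firm count of affected patients.** Section 12.4 puts about 30% of prescriptions as not or only somewhat indicated. One might take the other 70% of 600 = 420 as justified, assume 20-30% of them somewhat too broad, and arrive at 84-126 per arm. That ignores unratable cases and the BV-below-35 diversion, rests on an assumed share, and counts differently worded advice rather than changed prescriptions.
- **Patients already affected.** Section 4.1 reports pilot-phase experience, and section 5 says pilot participants are not randomized. The protocol does not show that any randomized patient has received the differing advice.

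It is also fair that recommendations are not binding (10.1, 14.5) and that secondary outcomes are analysed descriptively (12.9). Both limit the consequence; neither explains the discrepancy.

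**Conclusion.** The discrepancy is real and visible on the page: three of five rows of a BV-independent table differ between arms without explanation. For patients who continue antibiotics, part of the difference in advice comes from allocation and not from the BV result. The point bears on attribution for reserve or restricted antibiotic use, adherence and the per-protocol set. Some of any observed difference may still be BV-driven, because BV controls entry to the experimental choice table. The claim is only that a difference can arise without BV and could not then be separated from it.

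The 1-9 percentage point range rests wholly on assumed values of q and d, including the assumption that the firmer wording has the higher uptake. The finding itself depends only on the wording of the two tables.

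**What to change.** Reconcile 8.9 and 8.10 by using a single choice-of-antibiotic table in both arms, with the same wording and recommendation grades. The arms would then differ only where the BV result enters. Which wording to adopt is for the sponsor to decide. Flag any patients randomized before the change so that reserve-antibiotic, adherence and per-protocol results can be examined with and without them.

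If the difference is intended as part of the intervention, the protocol should say so and limit its conclusions on these outcomes to the matrix as a whole.

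The cost is small: an amendment to one table and an updated recommendation template, with no additional data or visits.

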8.10 Antibiotic treatment decision procedure specific to the experimental group

The result of the BV test will be unmasked for the investigators and combined with the prescription assessment form using the decision matrix below. The final recommendation (to stop, continue or change antibiotic treatment) will be shared with the treating team.

Necessity of antibiotics	BV score < 35	BV $\geq 35 \leq 65$	BV > 65
Clearly not indicated	STOP*	STOP*	Expert consultation
Somewhat indicated	STOP*	STOP**	Continue ***
Justified	Expert consultation	Continue ***	Continue ***
Cannot be rated	STOP*	STOP**	Continue ***

*Strong recommendation; **Moderate recommendation; ***review choice of antibiotic

In all cases of “continue antibiotic treatment***”, rate the choice of antibiotic. The final recommendation (to stop, continue or change the antibiotic) will be shared with the treating team.

Choice of antibiotic:	Recommendation
Far too broad	Change drug
Somewhat too broad	Change drug
Appropriate choice	Continue same drug
Somewhat too narrow	Change drug
Cannot be rated	Expert consultation

8.11 Table 1 Data Collection

At enrollment
Demographics: Age, sex, gender, ethnicity
Admission data: Date of admission to hospital, date of admission to ICU
Reason for admission to hospital, reason for admission to ICU
Comorbidities (diabetes, cardiovascular, liver, renal, ...)

Antibiotic prescription: name of drug, dose, start and end date Suspected/confirmed Diagnosis (according to treating team)
Clinical status: Vital signs, temperature (T max day -2 to Day 1), ventilation status; Need for vasopressor support (type and dose)
Data on infection: Site, Microbiological results Signs and symptoms of infection
Basic laboratories: Hematological, biochemical (routine)
Imaging: Pertinent Xray, CT scans
Baseline status of MDRO colonization: swab results for MRSA, VRE, CPE
During study period
Antibiotics prescribed (start and end dates, name, dose)
Antibiotic treatment recommendation, date of recommendation, adherence to recommendation
Microbiological results
Colonization status for MDRO
New signs and symptoms of infection
Adverse events related to antibiotics
Laboratory values for creat, liver, hematology
End of study
Vital status: date of death, date of discharge from ICU, date of discharge from hospital Disposition upon discharge from ICU Final clinical outcomes and DOOR ranking

9. CLINICAL AND LABORATORY EVALUATIONS

9.1 Clinical Evaluations

After informed consent has been obtained, a research member with appropriate training will record the listed information on the eCRF. The initial evaluation will document reasons for ICU admission, current presentation and symptoms, working diagnosis, the reason for antibiotic therapy, and results of laboratory and diagnostic investigations. Patients will be monitored for 28 days or until death, with an End of Study Visit (EOSV) conducted at the conclusion.

Data collected during follow-up visits will include antibiotic prescriptions, symptoms of infections, laboratory and radiological results from the treating team, and adverse events. Antibiotic data will be extracted from the APSS (Lumed) application, while clinical diagnosis and evolution data will be sourced from patient charts and direct observation. Adverse events will be reported as part of the primary safety outcome.

All data will be collected on an electronic case report form (CRF). Original study forms (source documents) will be kept on file at the study site. All data will be kept for at least 7 years after the study's close.

9.2 Schedule of Clinical Evaluations and Data Collection

	Clinical data	Laboratory data	Microbiological data	Radiological data	Antibiotic use data
Baseline	Signs and symptoms of infection; syndrome	MeMedBV; CRP and PCT if collected by treating team	Micro collected since enrollment by treating team	Pertinent radiological findings if available	Start dates for all antibiotics prescribed since enrollment
Day 3	New signs of infection	Standard of care (if available: CBC, SMA-7, LFTs, CRP, PCT)	Results of all Micro cultures collected since enrollment)	findings pertinent for source of infection	Start and end dates for all antibiotics; follow-up adherence to treatment recommendation
Day 7	New signs of infection Or adverse events from antibiotics	Standard of care (if available: CBC, SMA-7, LFTs, CRP, PCT)	Results of all Micro cultures collected since enrollment)		Start and end dates for all antibiotics
Day 14	New signs of infection or adverse events from antibiotics	Standard of care (if available: CBC, SMA-7, LFTs, CRP, PCT)	Results of all Micro cultures collected since enrollment)	Imaging findings pertinent for new infection or source of initial infection	Start and end dates for all antibiotics
Day 28 +/- 2	Outcome Status	Standard of care (if available: CBC, SMA-7, LFTs, CRP, PCT)	Results of all Micro cultures collected since enrollment)	Start dates for all antibiotics prescribed since enrollment	Start and end dates for all antibiotics

Obtain blood sample; freshly collected sample should be processed (clotting, centrifugation and serum separation) **within two hours for testing (see lab manual)**.

9.3 Specimen Collection and Laboratory Evaluations

Personnel who collect specimens from participants must use personal protective equipment (PPE) in accordance with their institution guidelines. Collection kits will be provided to participating sites along with a laboratory manual describing the collection of quality samples as well as instructions for specimen processing, safe storage requirements and packaging to the research lab for analysis.

Aside from the initial BV testing, the study team will not request any additional blood work but will collect data on laboratory, microbiological and pertinent radiological findings requested by the treating team.

The initial blood tests requested for BV testing will be collected from all participants on enrollment day. Testing will be performed according to the manufacturer's instructions in the research space of the M14 CRP (see lab manual). The personnel performing the measurements will be blinded to clinical information and results of other investigations. Within 24 hours of testing, BV results will be provided to the study team only for the intervention group; results of the control group will remain hidden. All lab materials used for this testing will be supplied by research funds.

9.3.1 Research Blood Collection Serum Specimen

Blood will be collected in 1 x 6mL yellow top SST vacutainer on Enrollment. Study personnel will collect equal amounts of serum into pre-labelled 2 mL cryovials. Research blood samples should be processed within two hours for testing. Detailed instructions for the collection, storage and shipment of the serum samples are provided in the Laboratory Manual.

10. RISK MANAGEMENT

10.1 Risk Management

We have implemented several procedures to minimize potential risks to participants. These include:

- Specific study inclusion and exclusion criteria to minimize risks for specific high-risk populations
- Participants will have one additional blood sample (about 3-5mL) to be combined with usual bloodwork, on the day of enrollment. The risk of blood sampling includes bleeding, bruising and pain at the drawing site. These risks will be reduced by trying, as much as possible, to collect blood when other standard of care blood tests are being collected.
- The study ensures that standard of care is provided to all participants, with the clinician making final treatment decisions. While the study team's recommendations on antibiotic therapy may inform the treating team, they are not obligatory. The study team mitigates risks associated with potentially insensitive or non-specific biomarker assessments by prioritizing clinical judgment and suggesting expert consultations in cases of significant discrepancies.
- Confidentiality risks are minimized by coding participant information and securely storing it in compliance with MUHC REB policies.

11. EVALUATION, RECORDING, AND REPORTING OF ADVERSE EVENTS

In this RCT, the primary safety outcome will encompass all significant potential adverse events related to the cessation or withholding of antibiotics. These adverse outcomes will be integrated into the primary safety outcome measure and will not be reported separately as Adverse Events (AEs) or Serious Adverse Events (SAEs) elsewhere in the study.

Despite our comprehensive approach, unforeseen adverse events may still occur. Therefore, ongoing monitoring of AEs is essential to ensure participant safety and maintain data integrity.

11.1 Definitions

11.1.1 Adverse Event (AE)

An AE is any untoward medical occurrence in a participant or clinical investigation participant, administered a study medication/intervention (e.g., recommendation for antibiotic cessation), which does not necessarily have a causal relationship with this treatment. An AE can therefore be any unfavorable and unintended sign (including an abnormal laboratory finding), symptom, or disease temporally associated with the use of a medicinal (investigational) study medication/intervention, whether related to the medicinal (investigational) study medication/intervention.

